5.1 Variables

The PK variables of interest are:

- AUClast: the AUC from time zero to the last measurable concentration sampling time (tlast)
- Cmax: The maximum (peak) observed plasma drug concentration after single-dose administration
- Tmax: The time to reach maximum (peak) plasma drug concentration after single dose administration (time)

5.2 Descriptive analyses

HSY244 plasma concentration data will be listed by treatment, participant, and visit/sampling time point. Descriptive summary statistics will be provided by treatment and visit/sampling time point, including the frequency (n, %) of concentrations below the LLOQ and reported as zero.

Summary statistics will include mean (arithmetic and geometric), SD, CV (arithmetic and geometric), median, minimum, and maximum. An exception to this is Tmax where median, minimum, and maximum will be presented. Concentrations below LLOQ will be treated as zero in summary statistics and for PK parameter calculations. A geometric mean will not be reported if the dataset includes zero values. Pharmacokinetic parameters will be calculated as described in Section 5.1 and will be listed by treatment and participant. Additional parameters may be estimated as relevant. Graphical methods will be employed to show mean and individual concentration-time profiles.

5.3 Statistical model, assumptions and hypotheses

Not applicable

6 Statistical methods for Pharmacodynamic (PD) parameters

6.1 Primary objective

The primary objective is to evaluate the efficacy of HSY244 to restore sinus rhythm in participants with AF.

6.1.1 Variables

The primary endpoint will be conversion to sinus rhythm for at least one minute within 90 minutes after the start of study drug administration (yes or no). Only participants that complete treatment will be included in the primary analysis. If a participant has been monitored for at least 45 minutes and is not converted to sinus rhythm, the primary endpoint will be defined as

| Novartis | For business use only | Page 9 |
|----------|-----------------------|--------------|
| SAP | | CHSY244X2201 |

'no'. If a participant converts to sinus rhythm at any time during the post-treatment 90 minutes observation period, regardless of the length of time monitored, the primary endpoint will be defined as 'yes'. Participants with a non-missing primary endpoint value will be included in the primary analysis regardless of their study disposition e.g. loss to follow up, early termination, etc.

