### **6.2.3 Rescue medication**

In the case that a participant should still be in AF at 90 minutes after study drug administration, direct current cardioversion may be applied unless deemed inappropriate by the Investigator.

If the participant develops a new clinically or hemodynamically significant arrhythmia, medically appropriate direct current cardioversion, defibrillation, or anti-arrhythmic pharmacotherapy should be initiated at the Investigator's discretion. Alternatives should be considered for the medications on the prohibited medication list ([Table 6-2](#)) within the study treatment period.

If the participant develops a seizure or other neurological symptom, medically appropriate therapy should be initiated at the Investigator's discretion. Alternatives should be considered for the medications on the prohibited medication list ([Table 6-2](#)) within the study treatment period.

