## 8.3 Efficacy

The primary efficacy measure is defined as conversion from AF to sinus rhythm, sustained for at least 1 minute during the 90 minutes after the start of the study drug administration, as assessed on the study Holter monitor. After 90 minutes, all participants may undergo direct current cardioversion if they remain in persistent AF, unless deemed inappropriate by the Investigator.

The Investigator should record periods in AF or sinus rhythm during the first 90 minutes after study drug administration, CCI and time of direct current cardioversion (if occurs, unless deemed inappropriate by the Investigator).

Blood and urine samples will be collected at the time points defined in the Assessment Schedule ([Table 8-1](#)). Follow instructions outlined in the manual provided by the designated CRO regarding collection, numbering, and processing.

Results need to remain blinded during the study.

Commercially Confidential Information

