1.4 Study design and treatment

This is a randomized, placebo-controlled, investigator- and participant-blinded study to evaluate the efficacy, safety, tolerability, and pharmacokinetics of HSY244 in participants with AF. An initial cohort (Cohort 1) of approximately 29 participants (approximately 20 participants receiving HSY244) is planned to be enrolled to evaluate a single 150 mg i.v. dose of HSY244 for AF cardioversion to sinus rhythm.

Commercially Confidential Information

Participants with AF that meet clinical criteria for direct current cardioversion will be screened, and on Day 1, after eligibility is confirmed, administration of a 15 minute i.v. infusion of HSY244 or placebo will occur. Participants will then be monitored for cardioversion to sinus rhythm. For those remaining in AF after 90 minutes, direct current cardioversion can be performed. Participants will be monitored for at least 3 hours, although overnight observation will be available. Participants will be evaluated for safety and pharmacokinetic assessments during end of study assessments, which are to occur on Day 5 (96 hours post dose) \pm 24 hours.

2 First interpretable results (FIR)

First interpretable results (FIR) will be provided for this trial. Commercially Confidential Information

The FIR will focus on the following analyses:

- 1. Participant Disposition
- 2. Demographics and baseline characteristics by cohort. Baseline characteristics include, but not limited to: age, sex, race, ethnicity, BMI, relevant medical history/current medical conditions (previous diagnosis of heart failure, etc.), duration of current AF episode, etc.
- 3. Safety Results
 - a. Number and percentage of adverse events by body system and Cohort
 - b. Number and percentage of adverse events by preferred term and Cohort
- 4. Pharmacokinetic results for each Cohort
- 5. Pharmacodynamic analyses include, but are not limited to:
 - a. Fisher's exact test comparing conversion rates between HSY244 and placebo
 - b. MMRM analysis of ECG and heart rate parameters comparing HSY244 and placebo
 - c. Concentration effect analysis of QT and Heart Rate parameters
 - d. Time to event analysis for the time to conversion and time in sinus rhythm after conversion comparing HSY244 and placebo
 - e. AF burden comparison between HSY244 and placebo

3 Interim analyses

4 Statistical methods: Analysis sets

For all analysis sets, participants will be analyzed according to the study treatment(s) received.

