6.1.2 Descriptive analyses

The observed proportion of participants converted to sinus rhythm within the first 90mins of observation will be reported for each treatment and cohort. The observed proportion of participants that are electrcardioverted after the 90mins observation period will also be reported for each treatment and cohort.

Commercially Confidential Information

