7.2 Descriptive analyses

Participant demographics and other baseline characteristics

Demographic and other baseline data including disease characteristics will be listed and summarized descriptively by treatment group and cohort for the safety analysis set.

Categorical data will be presented as frequencies and percentages. For continuous data, mean, standard deviation, median, minimum, and maximum will be presented.

Relevant medical histories and current medical conditions at baseline will be summarized by system organ class and preferred term by treatment group and cohort. For AF disease history, if the start month is missing, then the start month will be imputed as 'JAN'. Similarly, if the start day is missing, the start day will be imputed as '01'.

Treatment

Data for study drug administration (rescue medication), concomitant medications and significant non-drug therapies prior to and after the start of the study treatment will be listed and summarized according to the Anatomical Therapeutic Chemical (ATC) classification system by treatment group and cohort.

Vital signs

All vital signs data will be listed by treatment group, cohort, participant, and visit/time and if ranges are available, abnormalities (and relevant orthostatic changes) will be flagged. Summary statistics will be provided by treatment, cohort and visit/time.

ECG evaluations

- 1. PR, QRS, QT, QTcF, and RR intervals will be obtained from single time point ECGs for each participant during the study. ECG data will be read and interpreted locally for initial safety readouts. The single time point ECGs will be read centrally for the parameters above and these will be reported in the CSR.
- 2. Categorical Analysis of QT/QTcF interval data based on the number of participants meeting or exceeding predefined limits in terms of absolute QT intervals or changes from baseline will be presented. In addition, a listing of these participants will be produced (by treatment group).

QT/QTcF and QRS duration will be examined separately between individuals with and without a complete bundle branch block.

All ECG data will be listed by treatment group, cohort, participant, and visit/time, and abnormalities will be flagged.

Summary statistics will be provided by treatment, cohort and visit/time.

Commercially Confidential Information

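### SAP 6.1.1 analyses completers monitored for under 45 minutes only if they converted, and its rule for success does not require conversion to precede an in-window shock or antiarrhythmic drug (minor)

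*SAP*

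**What the plan says.** SAP 6.1.1 restricts the primary analysis to participants who complete treatment. It defines the endpoint as one minute or more of sinus rhythm within 90 minutes of starting study drug. Three rules follow.

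- *No* is assigned on this condition: "If a participant has been monitored for at least 45 minutes and is not converted to sinus rhythm".
- *Yes* is assigned on this one: "If a participant converts to sinus rhythm at any time during the post-treatment 90 minutes observation period, regardless of the length of time monitored".
- Inclusion: "Participants with a non-missing primary endpoint value will be included in the primary analysis regardless of their study disposition".

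Protocol 12.4.4 states a different inclusion criterion, completion of the Day 1 assessments, and expects few missing data.

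On rescue, Protocol 6.2.3 says that for a new significant arrhythmia "medically appropriate direct current cardioversion, defibrillation, or anti-arrhythmic pharmacotherapy should be initiated" at the Investigator's discretion. Protocol 6.6.2 says much the same, and neither sets a time limit. Planned direct current cardioversion for persisting AF is available from 90 minutes (Protocol 3).

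Protocol 8.3 describes the efficacy measure as "conversion from AF to sinus rhythm, sustained for at least 1 minute during the 90 minutes after the start of the study drug administration". SAP 6.1.2 adds: "The observed proportion of participants that are electrcardioverted after the 90mins observation period will also be reported". Protocol 12.4.3 (intercurrent events) and 12.4.5 (sensitivity analyses) are marked not applicable. Protocol 12.4.6 plans a supplementary Fisher's exact test in everyone dosed.

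**The concern.** There are two gaps in how the primary endpoint is scored.

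First, below 45 minutes of monitoring, whether a completer is analysed depends on the outcome. A converter has a value. A non-converter fits neither rule, has no value and drops out.

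Second, the *yes* rule is silent on what produced the sinus rhythm. Read literally, a participant shocked at 60 minutes for a new arrhythmia, who then has a minute of sinus rhythm before 90 minutes, is a success for the assigned arm. The objective (SAP 6.1) is the efficacy of HSY244 in restoring sinus rhythm, so this would score the wrong thing.

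If such a case occurred, its scoring would have to be settled after the event. In an arm of 5 to 9 participants, that decision could change the reading of the primary result.

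**Working it through.** **Step 1. Apply the SAP 6.1.1 rules to completers.**

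| Monitored | Converted | Value | Analysed |
|---|---|---|---|
| 45 min or more | yes | *yes* | yes |
| 45 min or more | no | *no* | yes |
| under 45 min | yes | *yes* | yes |
| under 45 min | no | none assigned | no |

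The last row is inferred from the three rules together; the SAP does not say it in words.

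**Step 2. Arm sizes.** The documents give about 29 randomised, about 20 on HSY244, and a 5:1 ratio. Taking 20 of 29 leaves 9 on placebo. Taking 29 at 5:1 gives 29 × 5/6 = 24.2 and 29/6 = 4.8, so about 24 and 5. Both splits are used as a range. Converter counts below are assumptions. Fisher p-values are two-sided, also an assumption, since the visible text gives no sidedness.

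**Step 3. One short-monitored non-converter left out.**

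- HSY244: 8/20 = 40.0% becomes 8/19 = 42.1%; 10/24 = 41.7% becomes 10/23 = 43.5%.
- Placebo with one converter: 1/9 becomes 1/8, so the difference from 8/20 goes from 28.9 to 27.5 points. With 1/5 becoming 1/4, the difference from 10/24 goes from 21.7 to 16.7 points.
- Placebo with no converter: 0/9 becomes 0/8. The difference from 8/20 stays at 40.0 points, but p goes from 0.033 to 0.063.

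Omission on HSY244 widens the difference; omission on placebo narrows it or leaves it unchanged.

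**Step 4. Is scoring these participants *no* closer to the truth?** Let p be the true 90-minute rate, q the share lost before 45 minutes, and f the share of conversions that precede loss, with loss unrelated to conversion. Then:

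- SAP rule = [(1−q)p + qfp] / [(1−q) + qfp]
- scored *no* = (1−q)p + qfp

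Assume p = 0.40 and q = 0.10.

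- f = 0.50: SAP rule (0.36 + 0.02)/(0.90 + 0.02) = 41.3%; scored *no* 38.0%.
- f = 0.75: SAP rule (0.36 + 0.03)/(0.90 + 0.03) = 41.9%; scored *no* 39.0%.

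Scoring *no* is closer only if f exceeds about 0.61. Kaplan-Meier returns the true rate in both cases: 1 − (0.80)(1 − 0.20/0.80) = 40.0% and 1 − (0.70)(1 − 0.10/0.70) = 40.0%.

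**Step 5. The rule from 45 to 89 minutes works the other way.** Non-converters whose monitoring ends in that interval are scored *no*, although they could still have converted. With 10% lost there and 75% of conversions already seen, the rate is 0.9 × 0.40 + 0.1 × 0.30 = 39.0% against a true 40%.

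**Step 6. One rescued participant scored *yes*.**

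| Counts, HSY244 vs placebo | Difference (points) | p |
|---|---|---|
| 8/20 vs 0/9 | 40.0 | 0.033 |
| 8/20 vs 1/9 (placebo rescued) | 28.9 | 0.20 |
| 9/20 vs 0/9 (HSY244 rescued) | 45.0 | 0.027 |
| 10/24 vs 0/5 | 41.7 | 0.13 |
| 10/24 vs 1/5 (placebo rescued) | 21.7 | 0.62 |
| 11/24 vs 0/5 (HSY244 rescued) | 45.8 | 0.13 |

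The shift is 1/9 = 11.1 to 1/5 = 20.0 points for a placebo case, and 1/24 = 4.2 to 1/20 = 5.0 points for an HSY244 case.

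**The case against.** **Exposure is small.** The Holter runs for 24 hours, participants rest for 2 hours and are observed for at least 3 hours (Protocol 3), and Protocol 12.4.4 expects minimal missing data. The 10% loss in step 4 is illustrative. This stands, and it is the main reason the point is minor.

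**Intent on rescue is fairly clear.** The measure is conversion from AF, the objective concerns what HSY244 does, and electrical cardioversion is reported separately. A severe or serious event during the infusion also stops the infusion (Protocol 9.1.1) and so removes the participant from the primary analysis. A reader might infer that the plan means to count shock-induced rhythm as success; the documents do not support that. But SAP 6.1.2 separates only shocks after 90 minutes, and a rescue between the end of infusion and 90 minutes has no visible scoring rule.

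**Scoring short-monitored non-converters *no* is not a correction.** A reader might infer that it is less biased. Step 4 shows that it need not be, and the visible text gives no timing of conversions to settle it.

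**Part of the text is redacted.** The analysis-set sections (Protocol 12.1, SAP 4) are cut after the PK set, and SAP 7.1 mentions a PD analysis dataset with no visible definition. There is also a redaction just before the completer sentence in Protocol 12.4.2. SAP 6.1.3.3 shows only a heading, and SAP 6.1.3.4, 6.3.3 and Table 4-1 are not visible. A relevant rule may sit there. SAP 6.1.1 itself shows no redaction, so at the least a cross-reference is missing.

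**Conclusion.** Both gaps hold on the visible text, and the point is minor. Inclusion under 45 minutes depends on outcome and can raise an arm's observed rate (by about 2 points per HSY244 case in the examples) or leave it unchanged when the arm has no converters. The *yes* rule does not exclude sinus rhythm after an in-window rescue. One such placebo case is worth 11 to 20 points, one HSY244 case 4 to 5.

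A reader might infer that the rules favour HSY244. They do not do so systematically: the two monitoring rules pull in opposite directions, either arm may be affected, and a rescued placebo participant scored *yes* shrinks the difference. The net effect has no fixed sign.

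The sizes rest on assumed converter counts and on 5 to 9 placebo participants. The documents give no rate of short monitoring or of in-window rescue. The Kaplan-Meier result also assumes that loss of monitoring is unrelated to conversion.

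**What to change.** Before unblinding, amend SAP 6.1.1. These changes concern scoring only.

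1. Define *yes* as one minute or more of sinus rhythm on the study Holter, within 90 minutes of the start of study drug administration, and before any shock, defibrillation or antiarrhythmic rescue. Score participants rescued before conversion *no*. Apply the same scoring in the all-dosed supplementary analysis (Protocol 12.4.6).
2. SAP section 2, item 5d already plans "Time to event analysis for the time to conversion and time in sinus rhythm after conversion comparing HSY244 and placebo". From it, report a Kaplan-Meier 90-minute conversion estimate by arm as a sensitivity analysis. Censor at end of monitoring and keep rescued participants as non-converters to 90 minutes.
3. Optionally, report the result with short-monitored non-converters scored *no*, labelled as a conservative bound and not as a less biased estimate.
4. Reconcile the inclusion rule with Protocol 12.4.4 and with any redacted PD analysis set.

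If redacted text already covers any of this, a cross-reference from 6.1.1 is enough.

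The cost is a few sentences and one estimate from a planned analysis. Protocol 8.3 has rhythm periods and the time of direct current cardioversion recorded. SAP 7.2 lists "Data for study drug administration (rescue medication), concomitant medications and significant non-drug therapies prior to and after the start of the study treatment", but the visible text does not confirm that clock times of antiarrhythmic drugs are captured; item 1 needs them, so this should be checked. The observed rate may come out slightly lower.

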6.1.2 Descriptive analyses

The observed proportion of participants converted to sinus rhythm within the first 90mins of observation will be reported for each treatment and cohort. The observed proportion of participants that are electrcardioverted after the 90mins observation period will also be reported for each treatment and cohort.

Commercially Confidential Information

6.1.3 Statistical model, assumptions and hypotheses

The conversion rates between HSY244 and placebo will be compared using Fisher's Exact test. This will test a null hypothesis that the conversion rate is the same for HSY244 and placebo. The conversion rates for each treatment and the exact 80% confidence intervals will be reported. The difference in the conversion rates between HSY244 and placebo will be reported along with the 80% confidence limits for the difference, as well as the odds ratio, the 80% CI for the odds ratio, and the associated p-value.

The impact of duration of current atrial fibrillation episode (< 48 hours, 48 hours - 7 days, 7 - 14 days, 14 - 30 days, and 30-60 days) on conversion rate will be investigated in a supporting analysis. The impact of length of time of known atrial fibrillation diagnoses on conversion rate will also be explored in a supporting analysis (e.g. < 1 year, 1 - 5 years, 6 - 10 years, >10 years, and quartiles of length of atrial fibrillation diagnosis).

All analyses will be performed separately for Cohort 1 CCI Placebo participants from the two cohorts may be pooled for summaries and analyses if it is deemed appropriate. Only participants who complete study treatment will be included in the primary analysis.

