The participant should be monitored for at least 180 minutes (3 hours), after study drug administration for safety and blood sampling; this monitoring period can be extended through 24 hours if deemed necessary or appropriate by the Investigator and/or for convenience for the participant. The participant can be transferred to other locations within the study site (i.e., to a post-anesthesia care unit [PACU], hospital ward, or clinical trials unit given site staff is appropriately trained) during the 3 hour monitoring period (or for 24 hours if observation period is extended), at the discretion of the Investigator, as long as the participant can remain undisturbed (i.e., remain in supine/semi-recumbent position for the first 2 hours), and the study protocol requirements, assessments and appropriate standard clinical care practices are possible.

Commercially Confidential Information

If the participant remains on-site overnight, Day 2 (24 hours post-dose) assessments should be completed before the participant's release from the study site. If the participant does not remain at the site overnight, the site will call the participant on Day 2 (24 hours post dose  $\pm$ 4 hours) to check on AEs, as well as to guide the participant for the removal of the Holter device. The participant should remain resting in a supine or semi-recumbent position for at least 15 minutes prior to the removal of the Holter (continuous ECG) monitor to allow for the assessment of resting heart rate CCI. The participant is required to return to the study site within  $\pm$ 24 hours of Day 5 (96 hours post dose) for end of study (EOS) assessments.

A total of approximately 29 participants are planned to be randomized in Cohort 1, of which approximately 20 will receive HSY244. Participants will be randomized in a 5:1 HSY244-to-placebo ratio.

Commercially Confidential Information

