## 5 Study Population

The study population will include hemodynamically stable men and women between 18 and 80 years of age with a clinical indication for direct current cardioversion of AF, with the current AF episode lasting between 6 hours and 60 days. In Cohort 1, a total of approximately 29 participants with AF will be randomized, of which approximately 20 will receive HSY244.

Commercially Confidential Information

Replacement participants will be allowed for those participants who discontinue study drug administration before completion if those participants have not discontinued due to adverse drug reactions or adverse events from study procedures. A maximum of 4 replacement participants will be allowed per Cohort. Please refer to [Section 9.2](#) for additional details. Rescreening of screen failures will be allowed. Please refer to [Section 8.1](#) for additional details.

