#### **12.4.2 Statistical model, hypothesis, and method of analysis**

The conversion rates between HSY244 and placebo will be compared using Fisher's Exact test. This will test a null hypothesis that the conversion rate is the same for HSY244 and placebo. The difference in the conversion rates between HSY244 and placebo will be reported along with the 80% confidence limits for the difference, as well as the odds ratio, the 80% CI for the odds ratio, and the associated p-value.

Results will be displayed tabular and graphically, where the conversion rate (80% CI) for each treatment will be displayed in dot plots and a forest plot.

The impact of duration of current atrial fibrillation episode (< 48 hours, 48 hours - 7 days, 7 - 14 days, 14 - 30 days, and 30 - 60 days) on conversion rate will be investigated in a supporting analysis..

Commercially Confidential Information

Only participants who complete study treatment will be included in the primary analysis.

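### Fisher's exact test is valid but conservative for the primary comparison; Boschloo's exact test would be at least as powerful at the same level with the same participants

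*SAP*

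**What the plan says.** SAP 6.1.3 names one test for the primary endpoint: "The conversion rates between HSY244 and placebo will be compared using Fisher's Exact test". Protocol 12.4.2 agrees and adds "This will test a null hypothesis that the conversion rate is the same for HSY244 and placebo", which reads as two-sided. Neither public document shows a significance level, a sidedness or a success threshold. The sample size and interim sections are redacted, so these may exist out of view.

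The only visible guide to the level is the confidence coefficient. The SAP states "The conversion rates for each treatment and the exact 80% confidence intervals will be reported", and both documents plan 80% limits for the rate difference and the odds ratio.

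On arm sizes, Protocol section 3 says "A total of approximately 29 participants are planned to be randomized in Cohort 1, of which approximately 20 will receive HSY244" and, next to it, "Participants will be randomized in a 5:1 HSY244-to-placebo ratio". SAP 1.4 repeats the 29 and the 20. Protocol section 5 adds "A maximum of 4 replacement participants will be allowed per Cohort". The analysed set is restricted: "Only participants who complete study treatment will be included in the primary analysis". SAP 6.1.3 also lets placebo participants from two cohorts be pooled if that is judged appropriate.

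**The concern.** Fisher's test conditions on the total number of conversions. With a very small placebo arm, few tables are possible for each total, so the p-value moves in large steps and often cannot come close to the level. The test then rejects less often than its level allows, and power is lost with no benefit in validity.

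The design fixes the arm sizes but not the total number of conversions, so conditioning is a choice and not a requirement. An exact test without it is available. This is the only named test of the primary endpoint, in a small cohort that cannot afford to waste information.

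**Working it through.** **Inputs from the documents.** About 29 randomized, about 20 on HSY244, ratio 5:1, Fisher's exact test, 80% intervals.

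**Arm sizes.** The stated figures do not fit together:
- From 20 on HSY244 at 5:1: 20 × 6/5 = 24 in total, so 4 placebo. Adding the 4 permitted replacements gives 28, not 29.
- From 29 in total at 5:1: 29 × 5/6 = 24.2, so about 24 HSY244 and 5 placebo.
- By subtraction: 29 − 20 = 9 placebo.

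I therefore used three splits: 20:4, 24:5 and 20:9.

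**Assumptions.** The planning figures are redacted, so no stated power can be reproduced. I took one-sided 0.10 and two-sided 0.20 as the levels that match 80% intervals, and also ran one-sided 0.05 and 0.025 and two-sided 0.10 and 0.05. Conversion rates are illustrative: placebo 5% or 10%, HSY244 30% to 70%.

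**Method.** All 2×2 tables were enumerated for each split.
- Fisher one-sided p = hypergeometric probability of at least the observed number of HSY244 conversions, given the total. Two-sided p = sum over tables no more probable than the observed one.
- Boschloo p = maximum over the common rate π of P(Fisher p ≤ observed Fisher p | π), on a 1999-point grid.
- Size = maximum over π of the rejection probability when both arms share rate π. Power = product-binomial sum over the rejection region.

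Fisher's test is valid, so P(Fisher p ≤ c | π) ≤ c for every π. Boschloo's p-value is therefore never larger than the Fisher p-value it is built on, and it rejects every table that Fisher's test rejects.

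**One boundary by hand (24:5, no placebo conversions).** With m conversions, all on HSY244, Fisher one-sided p = C(29−m, 5)/C(29, 5), where C(29, 5) = 118,755.
- m = 8: 20,349/118,755 = 0.171
- m = 9: 15,504/118,755 = 0.131
- m = 10: 11,628/118,755 = 0.098

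At one-sided 0.10 Fisher's test needs 10 of 24 converters. Boschloo's test needs 8. At 20:4 the counts are also 10 and 8 (of 20). At 20:9 they are 6 and 5.

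**Results, Fisher to Boschloo.**

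| Split | Level | Maximum size | Power, 5% vs 40% | Power, 10% vs 50% |
|---|---|---|---|---|
| 20:4 | one-sided 0.10 | 0.042 to 0.096 | 0.20 to 0.48 | 0.39 to 0.61 |
| 24:5 | one-sided 0.10 | 0.042 to 0.099 | 0.40 to 0.65 | 0.52 to 0.71 |
| 20:9 | one-sided 0.10 | 0.046 to 0.090 | 0.68 to 0.79 | 0.72 to 0.83 |
| 20:4 | two-sided 0.20 | 0.103 to 0.192 | 0.20 to 0.48 | 0.40 to 0.61 |
| 24:5 | two-sided 0.20 | 0.144 to 0.191 | 0.53 to 0.64 | 0.63 to 0.66 |
| 20:9 | two-sided 0.20 | 0.112 to 0.178 | 0.73 to 0.79 | 0.75 to 0.83 |

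Over all 18 combinations of split and level, Boschloo's test rejects everything Fisher's test rejects plus 3 to 12 further tables, and its maximum size stays within the level.

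**Where the gain is small.** At 24:5, two-sided 0.20:
- 50% vs 5%: 0.77 to 0.80
- 50% vs 10%: 0.63 to 0.66
- 60% vs 5%: 0.90 to 0.91
- 60% vs 10%: 0.80 to 0.81

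The boundary moves from 9 to 8 of 24 with no placebo conversions, and stays at 14 with one. If the two-sided p-value is instead built by doubling the one-sided Boschloo p-value, the gain in these four scenarios is about 3 to 8 points. The construction matters.

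**The case against.** Fisher's test controls the type I error and is a standard choice for small tables. Conditional versus unconditional testing is a long-standing matter of preference. The public plan also leans towards estimation, with rates, a difference and an odds ratio all carrying 80% intervals, and it shows no go/no-go rule tied to this p-value. All of this stands: it makes the point an improvement in efficiency and not a flaw.

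A reader might infer three stronger things that the documents do not support.
- *That the placebo arm is 4 or 5.* No section says so. That count comes from the ratio, subtraction gives 9, and pooling placebo across cohorts could raise the number further.
- *That Fisher's test runs at less than half its level.* No level is public. The statement fits one-sided 0.10 (42% to 46% of the level). At two-sided 0.20 the size is 52% of the level at 20:4, 56% at 20:9 and 72% at 24:5.
- *That a real effect will be missed because of the test.* This needs a decision rule based on the p-value, and none is visible.

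Boschloo's test is not a full cure either. At one-sided 0.10 with a common rate of 5%, its own rejection probability is close to 0 at all three splits. It also leaves the planned intervals unchanged, so its p-value may disagree with the odds-ratio interval.

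**Conclusion.** The point holds as a cheap improvement. At every split and level tried, Fisher's maximum size is below the level. Boschloo's test, built on the same Fisher p-value, stays within the level and is never less powerful. That direction does not depend on the redacted level.

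The amount does depend on it. For 40% versus 5% conversion the gain is 11 to 28 points at one-sided 0.10 and 6 to 28 points at two-sided 0.20. It falls to about 1 to 3 points at 24:5, two-sided 0.20, once HSY244 converts at 50% or more. These figures rest on assumed levels and rates and on a placebo count that the documents leave unresolved, so no single gain should be quoted until the arm sizes are reconciled.

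**What to change.** Before unblinding, amend SAP 6.1.3 and add a matching note to Protocol 12.4.2:
1. Name Boschloo's exact unconditional test as the primary test, at the plan's own level.
2. State that level, the sidedness and, if two-sided, how the p-value is built. The guarantee of never losing power applies when the same two-sided Fisher p-value is used as the statistic.
3. Name an exact unconditional 80% interval method for the rate difference that is compatible with the test, and say how a disagreement with the odds-ratio interval will be reported.
4. Keep Fisher's p-value as a sensitivity result.
5. Reconcile the 29, the 20 and the 5:1 ratio, and give the intended placebo number.

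The cost is a few SAP sentences, a protocol note and a short validated program, with no extra participants or visits. The downsides are a less familiar test that does not condition on the total number of conversions, and a p-value that may not agree with the odds-ratio interval. The choice must be made before treatment codes are known, because changing the test afterwards would not be credible.
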